7.5.1. Acute Cellular Rejection

Acute Cellular Rejection will be graded based on ISHLT guidelines¹⁰³ described in **Table 4**.

ACR Grade	ACR Classification
A0	None
A1	Minimal
A2	Mild
A3	Moderate
A4	Severe

Table 4: Grading for Acute Cellular Rejection

Acute Cellular Rejection (Grade A2 or greater) will be treated based on IPLTC guidelines described in **Table 5**.

Table 5: Treatment for Acute Cellular Rejection

Initial Treatment	Methylprednisolone 10-20 mg/kg/day (max = 1 g/day) for 3 to 4 days AND return to maintenance steroid dosing
Repeat biopsy in 2-4 weeks depending on histology and/or clinical status (treatment success = ≤ A2)	
Persistent/Recurrent acute rejection*	Antibody-mediated rejection should be excluded If same or lower ACR grade (i.e. A3 to A2): Repeat high dose (IV) steroid protocol outlined in initial treatment. If worsening lung function and/or ACR grade, severe ACR (Grade A4) or failure of two courses of steroids: Rabbit (rATG): 1.5 mg/kg/day, (max 150 mg/day) for 10-14 days
Alternatives for refractory ACR	One or more of the following may be used: 1. Campath 1H (Alemtuzumab) 2. Total lymphoid irradiation 3. Photopheresis 4. Methotrexate 5. Rapamycin

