7.5. Diagnosis and Treatment of Rejection

Rejection will be defined according to the current ISHLT working formulation of pulmonary allograft rejection. Each transbronchial biopsy (TBBx) will be evaluated at the local center and all therapeutic decisions will be based on the local pathologist's findings.

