7.5.2. Antibody Mediated Rejection

Antibody Medicated Rejection (AMR) will be graded locally as shown in **Table 5**.

	DSA ¹ or Autoantibody	Abnormal Histology ²	Graft Dysfunction ³
I: Latent humoral response	X		
II: Subclinical humoral rejection	X	X	
III: Humoral rejection	X	X	X

¹ Circulating antibody to HLA or other antigens expressed in lung tissue.

² Including neutrophilic capillaritis or septal margination, high grade ($\geq A3$) or persistent / recurrent acute rejection, acute lung injury/diffuse alveolar damage, high grade (B2R) or persistent low grade (B1R) lymphocytic bronchitis, obliterative bronchiolitis, arteritis in the absence of acute rejection or other finding not explained by clinical circumstances (i.e. infectious causes thoroughly excluded)

³ Unexplained (i.e. infectious causes thoroughly excluded) persistent (> 1 week) change in respiratory status manifested by two MAJOR OR one MAJOR plus one or more MINOR criteria listed below:

MAJOR CRITERIA:

- I. Increase in resting respiratory rate $\geq 10\%$
- II. Decrease in resting SaO₂ $\geq 4\%$
- III. Persistent drop in FEV1 of $\geq 10\%$

MINOR CRITERIA:

- I. Daily repetitive cough
- II. Auscultatory findings
- III. Inadequate weight gain defined as a drop between 5-10 percentile points
- IV. CXR or CT changes

Table 5: Antibody Mediated Rejection Diagnostic Grading

Study participants will be screened for donor specific antibodies (DSA) monthly for the first 3 months following transplantation and then every 3 months if negative. C4d immunohistochemistry will be performed on all TBBx. AMR will be treated as described below.

I: Latent humoral response	No treatment, consider monitoring DSA more frequently
II: Subclinical humoral rejection	
 1. Administer methylprednisolone 10-20 mg/kg/day (max = 1 g/day) for 3 to 4 days AND return to maintenance steroid dosing. 2. Follow-up TBBx performed 2-4 weeks following completion of therapy. The local investigator may consider open lung biopsy if graft dysfunction is present. 3. If subclinical humoral rejection persists on the follow up biopsy, plasmapheresis will be performed.

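### In the Protocol's acute rejection rules, a repeat biopsy of grade A2 is at once a treatment success, a grade to be treated, and a persistent rejection to be retreated

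*Protocol*

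**What the plan says.** Three statements in Protocol 7.5.1 bear on grade A2. They concern the table headed Treatment for Acute Cellular Rejection, numbered Table 5 (the AMR grading table in 7.5.2 carries the same number).

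- Trigger: "Acute Cellular Rejection (Grade A2 or greater) will be treated based on IPLTC guidelines".
- Follow-up: "Repeat biopsy in 2-4 weeks depending on histology and/or clinical status (treatment success = ≤ A2".
- Persistent or recurrent rejection: "If same or lower ACR grade (i.e. A3 to A2" leads to "Repeat high dose (IV) steroid protocol outlined in initial treatment". The same row goes on to rabbit antithymocyte globulin for several situations, one being that two steroid courses have failed.

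Protocol 7.5 leaves the decision to each center: "all therapeutic decisions will be based on the local pathologist's findings".

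For AMR, footnote 2 to the grading table in Protocol 7.5.2 lists the findings that count as abnormal histology. One item is high-grade rejection (≥A3) or "persistent / recurrent acute rejection". The Study Definitions Page has the same item, and neither place defines persistent. Antibody alone is grade I; antibody plus abnormal histology is grade II; graft dysfunction in addition makes grade III. SAP 7.3.1 counts grade II or III, as reported locally under Protocol 7.5.2.

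**The concern.** A site holding a follow-up biopsy of A2 cannot follow all three statements. One calls the child a success, one calls the grade treatable, and one calls for another course. The label decides whether a second high-dose steroid course is given. It also decides whether the first course counts towards the two failed courses that open the next step. In a trial of immunosuppression these are substantial co-interventions, and seven sites may settle the matter in different ways.

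The same label may carry into an endpoint. If a repeat A2 is read as persistent rejection, an antibody-positive child can move from AMR grade I, which is not counted, to grade II or III, which is.

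**Working it through.** The plan gives no figure to reproduce here, so the check is mainly logical.

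**Step 1: where the rules overlap.** Inputs are the grades A0 to A4, the trigger (≥A2) and the success rule (≤A2), all from Protocol 7.5.1. Three first-biopsy grades lead to treatment (A2, A3, A4), and each can be followed by any of five repeat grades: 3 × 5 = 15 transitions.

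- Success rule met (repeat A0, A1 or A2): 3 × 3 = 9.
- Trigger met (repeat A2, A3 or A4): 3 × 3 = 9.
- Every transition meets at least one, so the number meeting both is 9 + 9 − 15 = 3.

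The three are A2 to A2, A3 to A2 and A4 to A2. All are same-or-lower transitions, which is the condition in the retreatment row, and A3 to A2 is that row's own example. If the row were confined to repeat biopsies that are not successes, its example could never reach it.

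**Step 2: which of these can change AMR incidence.** SAP 7.3.1 reports the proportion of subjects with an event, so a child already counted cannot be counted again.

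| Transition | Abnormal histology at first biopsy from the grade alone? | Can the reading of the repeat A2 change whether an antibody-positive child counts? |
|---|---|---|
| A2 to A2 | No | Yes, if there is no other abnormal histology |
| A3 to A2 | Yes (≥A3) | Only if antibody first appears between the biopsies |
| A4 to A2 | Yes (≥A3) | Only if antibody first appears between the biopsies |

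**Step 3: size per child.** Protocol 13.6 plans 25 per group. Assuming all 25 are in the analysis sample, one reclassified child moves that arm's AMR proportion by 1/25 = 0.04, or 4 percentage points. The documents do not allow the number of such children to be estimated. As context only, Protocol 2.4 reports pre-transplant autoantibodies to collagen V in 33% and to Kα1 tubulin in 44% of the earlier pediatric cohort, so antibody positivity itself is not rare.

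**Step 4: other analyses.**

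- Proportion with any Grade A rejection: unchanged, since the first biopsy already counts.
- Events per person-time for acute rejection and AMR (SAP 7.3.1): could change, depending on whether a repeat A2 is a new, continuing or resolved episode.
- Primary endpoint (SAP 7.2): does not use acute rejection grade.

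**The case against.** The strongest objection is that the endpoint effect is small and inferred. The AMR footnote does not cite the treatment table, and success there is a label for treatment response rather than a definition of persistence. Two of the three transitions start at ≥A3, which is abnormal histology on its own. This stands, and it limits the endpoint effect to the cases in step 2. The link rests on both places using the same term, and on the treatment table being the only visible text that gives the term content.

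A reader might infer that every antibody-positive child with a follow-up A2 switches from non-event to event; the ≥A3 criterion rules that out. A reader might also infer an effect on the humoral rejection stopping rule. The documents do not show one. Grade III also requires graft dysfunction, and under Protocol 12.8.2.2 the exact lower 95% limit must exceed 25% (Table 17 gives 9 of 20 as one such case).

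The retreatment row could be read as covering only a later recurrence. But its label includes persistent rejection, it directly follows the repeat-biopsy row, and the overlap of trigger and success rule at A2 would remain. Nor is retreatment simply left undefined: the table gives an instruction, and the trouble is that it conflicts with the row above.

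The extracted text may also be at fault. The conflict between trigger and success rule turns on the ≤ sign, and the asterisk on the persistent/recurrent label has no matching note in the text available. With a strict less-than sign that overlap would disappear, though the AMR criterion would still lack a definition unless the note supplies one. Both need checking.

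Finally, treatment is double-blind, so differing readings would not be expected to favour an arm, and SAP 7.3.1 adds an AMR evaluation under 2016 consensus criteria if the data allow. Both points soften the endpoint effect; neither resolves the table.

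**Conclusion.** The point holds as an internal contradiction in Protocol 7.5.1, minor in weight and cheap to repair. On the text as given, any repeat biopsy of A2 after treatment falls under three incompatible statements. Sites may therefore differ on retreatment and later escalation; the documents do not show that they will.

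The effect on AMR grade II or III is secondary. It assumes that persistent rejection means the same in the AMR criterion as in the treatment table. For incidence it is confined mainly to antibody-positive children going A2 to A2 without other abnormal histology, or whose antibody first appears between the biopsies, at 4 percentage points of an arm per child and in unknown number. The conclusion is subject to the check of the ≤ sign and the asterisk note.

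**What to change.** First check the ≤ sign and the asterisk note against the original document. Then the sponsor's clinical team should reconcile the trigger, the success definition and the retreatment row, so that a repeat A2 has one status; no threshold is proposed here. The abnormal-histology item in Protocol 7.5.2 (footnote 2) and on the Study Definitions Page should refer to that single definition of persistent or recurrent rejection. SAP 7.3.1 should then say whether a repeat A2 is a new or a continuing episode in the person-time rates.

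The cost is an amendment of wording with the usual ethics approval. Sample size and data collection do not change: Protocol 8.4 already has local biopsy readings recorded on the eCRF, so a blinded listing of repeat A2 biopsies with antibody status would show how many children are affected.

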7.5.2. Antibody Mediated Rejection

Antibody Medicated Rejection (AMR) will be graded locally as shown in **Table 5**.

	DSA ¹ or Autoantibody	Abnormal Histology ²	Graft Dysfunction ³
I: Latent humoral response	X		
II: Subclinical humoral rejection	X	X	
III: Humoral rejection	X	X	X

¹ Circulating antibody to HLA or other antigens expressed in lung tissue.

² Including neutrophilic capillaritis or septal margination, high grade ($\geq A3$) or persistent / recurrent acute rejection, acute lung injury/diffuse alveolar damage, high grade (B2R) or persistent low grade (B1R) lymphocytic bronchitis, obliterative bronchiolitis, arteritis in the absence of acute rejection or other finding not explained by clinical circumstances (i.e. infectious causes thoroughly excluded)

³ Unexplained (i.e. infectious causes thoroughly excluded) persistent (> 1 week) change in respiratory status manifested by two MAJOR OR one MAJOR plus one or more MINOR criteria listed below:

MAJOR CRITERIA:

- I. Increase in resting respiratory rate $\geq 10\%$
- II. Decrease in resting SaO₂ $\geq 4\%$
- III. Persistent drop in FEV1 of $\geq 10\%$

MINOR CRITERIA:

- I. Daily repetitive cough
- II. Auscultatory findings
- III. Inadequate weight gain defined as a drop between 5-10 percentile points
- IV. CXR or CT changes

Table 5: Antibody Mediated Rejection Diagnostic Grading

Study participants will be screened for donor specific antibodies (DSA) monthly for the first 3 months following transplantation and then every 3 months if negative. C4d immunohistochemistry will be performed on all TBBx. AMR will be treated as described below.

I: Latent humoral response	No treatment, consider monitoring DSA more frequently
II: Subclinical humoral rejection	
 1. Administer methylprednisolone 10-20 mg/kg/day (max = 1 g/day) for 3 to 4 days AND return to maintenance steroid dosing. 2. Follow-up TBBx performed 2-4 weeks following completion of therapy. The local investigator may consider open lung biopsy if graft dysfunction is present. 3. If subclinical humoral rejection persists on the follow up biopsy, plasmapheresis will be performed.
III: Humoral rejection	
 1. Pulse steroids (10 mg/kg) day 1-3. 2. Plasmapheresis x 5 days without IgG replacement. 3. Bortezomib (1.3 mg/M²) on days 1, 4, 8, & 11 (given after plasmapheresis) with IgG replacement after last dose of Bortezomib. 4. Rituximab (375 mg/m²) weekly weeks 1-4 for patients >1 month post-transplant.

Table 6: Treatment for Antibody Mediated Rejection

Subjects will be monitored for clinical improvement following treatment of AMR. Sites will consider repeat PRA for DSA at 1, 4 and 8 weeks post intervention and/or repeat biopsy for persistent symptoms.

7.5.3. Chronic Allograft Dysfunction

Chronic allograft dysfunction is defined as BOS, Grade 0p and above, or histologic evidence of obliterans bronchiolitis.^{103, 105} For participants old enough to perform spirometry, BOS will be diagnosed locally based on the 2001 ISHLT diagnostic criteria shown in Table 7. Local sites will rule out acute rejection, acute infection and airway stenosis or narrowing prior to diagnosing BOS. Spirometry will be supervised by a trained technologist at each site.

BOS Grade	Classification
0	FEV ₁ > 90% of baseline and FEF ₂₅₋₇₅ > 75% of baseline
0p	FEV ₁ 81 to 90% of baseline and/or FEF ₂₅₋₇₅ ≤ 75% of baseline
1	FEV ₁ > 66-80% of baseline
2	FEV ₁ > 51-65% of baseline
3	FEV ₁ > 50% or less of baseline

Table 7: Classification of BOS

For participants unable to perform a pulmonary function test, BOS will not be determined. Obliterative bronchiolitis (OB) will be used as the outcome in this population. OB will be identified by histology according to the ISHLT report.

Biopsy to evaluate for OB will also be obtained from participants with unexplained air trapping on high resolution expiratory CT images or ventilation perfusion scanning and participants with unexplained obstructive changes on infant PFTs.

Chronic allograft dysfunction will be evaluated and treated as described in **Table 8**.

BOS Grade 0p	
 1. Reassess for contribution of reflux and/or infection and treat as appropriate. 2. Perform bronchoscopy and transbronchial biopsy. 3. If no OB on transbronchial biopsy consider open lung biopsy if rapidly progressive and monitor study participant closely.
BOS progressing to Grade 1 despite above interactions	
 1. Reassess for ongoing contribution of reflux and/or infection and treat as appropriate. 2. Re-biopsy (transbronchial or open lung biopsy). 3. Pulse with steroids (Methylprednisolone 10 mg/kg/day x 3 days) and use cytolytic therapy (Thymoglobulin®) in patients with lymphocytic inflammation in active OB lesions.
Evidence of OB on biopsy	Pulse with steroids and use cytolytic therapy (Thymoglobulin®; dosing as above) in patients with lymphocytic inflammation in active OB lesions.

Table 8: Evaluation and Treatment for Chronic Allograft Dysfunction

Subjects will be re-evaluated every 3 months following the diagnosis of chronic allograft dysfunction. If BOS grade progresses the local PI may consider:

- Photopheresis
- Changing sirolimus to methotrexate (5-15 mg/M2 PO/IM weekly) for study participants who are not candidates for photopheresis.
- Re-transplant evaluation if consistent with local center guidelines.

7.5.4. Primary Graft Dysfunction

Primary Graft Dysfunction (PGD) will be evaluated at 4 time points as defined by the ISHLT Working Group on Primary Lung Graft Dysfunction.¹⁰⁷The ISHLT grading scheme for primary graft dysfunction (PGD) described in Table 9 is based on the P/F ratio and chest X-ray.

Grade	PaO ₂ /FiO ₂	Radiographic infiltrates consistent with pulmonary edema
0	>300	Absent
1	>300	Present
2	200-300	Present
3	<200	Present

Table 9: ISHLT Recommendations for Grading of Primary Graft Dysfunction (PGD) Severity

If multiple blood gas values are available, the worst P/F ratio will be used for the purposes of this grading scheme.

The following caveats to the grading scheme will be used.

- Absence of infiltrates on chest radiograph is Grade 0, even if PaO₂/FiO₂ ratio < 300.
- If the subject is on nasal cannula for oxygen of FiO₂ < 0.3, the subject is graded as 0 or 1, based on chest radiograph.
- Any subject on extracorporeal oxygenation is Grade 3.
- Any subject mechanically ventilated with FiO₂ > 0.5 on nitric oxide beyond 48 hours from the time of transplant is Grade 3.

8. Study Procedures

8.1. Enrollment

This research study will be explained in lay terms to each potential research participant. As the part of the informed consent process outlined in CFR Title 21 Part 50, the investigator or physician listed on the Investigator of Record (FDA 1572) will conduct a face-to-face meeting with the study candidate to review all required elements of informed consent. The potential study participant and/or parent/guardian will sign an informed consent form before undergoing any screening study procedures. Age of assent will be determined locally. Once the informed consent process is complete, the participant is considered enrolled in the study. All enrolled participants will be assigned a unique participant number and their disposition must be accounted for at the end of the study.

8.2. Screening/Baseline Visit

At the time of listing, potential participants will be entered on a site specific screening log. Age at listing, diagnosis and reason the patient was not enrolled into the study, if applicable, will be captured on the screening log. If the patient and/or parent(s)/guardian(s) are in agreement to participate in the study then the informed consent document should be obtained while the participant is on the wait list.

During the screening period study personnel will review the subject's medical record for previous and current medical history, perform a physical examination, and record the subject's demographic information (age, gender, and race). Blood specimens will be obtained for screening and mechanistic studies as specified in Appendix 1. Pre-transplant blood may be collected up to 60 days prior to transplant surgery. Blood must be recollected every 60 days until the transplant occurs.

The baseline visit will occur at the time of transplant. During the baseline visit, donor demographics (age, gender, and race), cause of death, HLA, Blood Type, serum creatinine, cytomegalovirus (CMV), Epstein - Barr virus (EBV), Hepatitis B, Hepatitis C, and HIV information will be collected.

8.3. Randomization

Eligibility for randomization will be confirmed. Hematology (CBC with differential and platelet count) and serum chemistries will be obtained within 2 weeks of randomization.

Randomization will occur within 12 hours after returning to the ICU following transplant.

Randomization will only occur if there are still spaces available at the time of transplantation. If the targeted accrual has been reached at the time of transplantation the participant will be excluded from further procedures and randomization.

8.4. Study Assessments

Subjects enrolled in this study will be followed for a minimum of 12 months post-transplant. Follow up visits will continue as detailed in Appendix 1 until the last participant completes 12 months of follow up (up to 54 months). Subjects may have blood and BAL samples collected at the following timepoints post-transplant:

- Transplant/Randomization-Day 0
- Day: 12
- Weeks: 4-6
- Months: 2, 3, 6, 9, 12, 18 and 24

Clinical safety will be monitored through routine physical examinations and appropriate laboratory assessments. During this period participants will have repeated clinical/laboratory evaluations, as specified in the Schedule of Events (Appendix 1, Schedule of Events- Recipient).

Assessments for the development of adverse events, serious adverse events, infections, rejections, death, PTLD, relisted for transplant or re-transplantation and hospitalizations will be completed at each study visit. All events will be reported using a designated electronic case report form (eCRF).

Chronic allograft dysfunction, relisting for transplant and death data will be collected up to 54 months post-transplant.

Protocol Biopsies

Transbronchial biopsies will be performed routinely as part of standard of care. The histologic evaluations from routine biopsies at day 12, week 4-6, month 3, month 6, month 12, month 18, and at the time of a symptomatic episode will be evaluated by the local pathologist and interpretations recorded on electronic case report forms (eCRFs).

Tacrolimus Standard Deviation Marker

Variability of tacrolimus will be monitored continuously starting 3 months post-transplant, using the calculation of the degree of fluctuation of tacrolimus blood levels over time, described by the standard deviation (SD) of tacrolimus levels.⁸² All outpatient levels obtained at least 3 months post-transplant will be used. In order to ensure the validity of tacrolimus trough levels, clinical sites will agree on quality control measures for obtaining trough levels. A rolling SD will be calculated for every patient using 1-year of tacrolimus levels (at least 3 trough levels). A SD of 2.0 or more (Shemesh et al. manuscript in preparation), an undetectable level or the absence of a tacrolimus trough level for 3 months will trigger a phone call among the site coordinator, the participant, parent(s)/guardian(s) and trained personnel at ISMMS to address barriers to adherence.

Individuals who meet the criteria listed below will not participate in the phone calls for the tacrolimus standard deviation marker:

1. Inpatient status
2. Any condition that, in the opinion of the investigator, may impact the quality or interpretation of the data obtained from the intervention.

The frequency of the calls is described in the table below.

Timepoint (following SD of 2.0 or more or undetectable level)	Call Frequency
Month 1	Weekly
Month 2	Monthly
Month 3-Month 24	Every other month

Table 10: Tacrolimus Standard Deviation Marker Call Schedule

Per the center clinician's discretion, calls may be escalated to 2 times per week for up to 1 month at any time during the intervention.

After one month, calls may revert to a weekly schedule for the following reasons:

- Participant discloses continuing non-adherence during the call;
- The most recent trough level is “undetectable”;
- The parent/guardian and/or team are concerned about ongoing non-adherence;
- A deterioration in medical outcomes as determined by the Center that is not explained by physiological factors;
- Per the clinical discretion of the call center staff member (i.e., the call center and parents/guardians are working on a remedy to an identified barrier).

The team at the call center will determine when the participant will return to the schema outlined in **Table 10**.

With the consent of the participant, information obtained during the intervention will be shared with the participant’s parent(s)/guardian(s) and clinical team.

Neurological Assessment

All participants who receive at least 1 dose of Rituximab (Rituxan®) or placebo will undergo a screening neurological exam at the time points specified in Appendix 1. Subjects who have objective findings will be evaluated by their local Neurology consult service.

